8.0. Data Protection and Confidentiality

All relevant national and local requirements regarding data protection, including GDPR and Health Research Regulations, will be adhered to. Patient data in OPTIMATE will be pseudonymized. Pseudonymity of patient data is assured by means of the unique study ID number allocated on enrolment. Throughout the study, participants will be identified by this study ID number. The master key that links clinical data to participants' identities will be stored securely in each study centre.

Participants will receive a copy of the Sponsor Data Protection Notice (DPN). The DPN will inform them of their rights about their data and provide contacts for Sponsor Data controller and Data protection commissioner.

Participants will also be informed that study monitors, representatives of the sponsor and the Ethics Committee may inspect their medical records to verify the information collected, and that all personal information made available for inspection will be handled in strictest confidence and in accordance with legal data protection requirements.

UCC research Data protection officer will review the protocol and study documents as required by UCC policies and procedures.

9.0 REC approvals and Governance

This trial has been reviewed by and received approval from the Clinical Research Ethics Committee of the Cork Teaching Hospitals the HSE South Eastern Area Research Ethics Committee for the University Hospital Waterford Centre and from the Commissie voor Medische Ethisiek van het UZ Gent/Committee on Medical Ethics Ghent University Hospital for Ghent University & Ghent University Hospital. A consent declaration was applied for, for the patients that lack decision-making capacity, through the Health Research Consent Declaration Committee (HRCDC). The application was made and conditional approval was granted on 17th July 2022. The PI has confirmed acceptance of the conditions.

In accordance with recommended practice relating to definitive clinical trials, the following oversight committees will be established for OPTIMATE: (i) Trial Management Group and (ii) Trial Steering Committee (TSC). The TMG will include the trial co-PI's, the UCC CRF-C director, the trial statistician and the trial manager. The TMG will meet formally monthly. Formal minutes of each TMG meeting will be kept and approved at each follow-on meeting. The TMG will address all matters relating to the preparation, organization, running and completion of OPTIMATE. The TMG will monitor patient recruitment and ensure that recruitment targets are achieved in order to avoid serious delays and avoidable deviations from the trial timeline.

The TSC will consist of two senior academic physicians in Geriatric Medicine and General Practice, a senior academic pharmacist and two non-clinical older persons (as per PPI description). There will be a gender balance within the TSC. The TSC will ensure a high standard of research and monitor the progress of the trial. It is proposed that the TSC will meet every 3 months and that all meetings will be minuted for the trial log. The TSC will also advise on dissemination of trial results.

A separate Data Monitoring Committee (DMC) is not considered necessary for the OPTIMATE trial because it is fundamentally a low-risk trial i.e. all advice points provided as part of the definitive intervention are evidence-based already, comply with current established best practice and are left

to the clinical judgement of the attending physician in terms of what to adopt or reject during medication review of patients enrolled in the trial. It is proposed that the TSC will also undertake the core roles and responsibilities of a DMC i.e. to regularly assess and advise on the data emerging from the trial, relevant safety data, the critical efficacy endpoints, and whether to recommend to the trial sponsor to continue, modify or stop the trial.

The entire OPTIMATE members will have up-to-date GCP training and certification (this is provided by the UCC CRF-C). The PI/coordinator will meet weekly with the trial manager to ensure that all current issues and project targets are discussed and achieved on time. All project targets (see Gantt chart) will be monitored closely by the PI/coordinator, the trial manager and a UCC CRF-C management team member.

The TMG will meet by teleconference on a monthly basis to discuss progress. There will be a rolling agenda with formal minutes to facilitate internal trial progress scrutiny. Issues relating to patient enrolment raised by primary researchers will form part of the monthly teleconference to ensure that any recurring or systematic problems relating to OPTIMATE trial recruitment are discussed comprehensively and corrected efficiently.

10.0 Insurance

The sponsor of the study, University College Cork, has appropriate insurance in place to cover litigation that may arise as a result of patients who are harmed as a result of participation in this trial.

11.0 Potential Risks of the intervention and the study procedures: (if applicable)

11.1 Adverse Event reporting (if applicable)

Adverse clinical events are expected to occur with a substantially high frequency in the patient population participating in OPTIMATE, given their age, comorbidity and frailty profile.

The definitive intervention (DI) to be deployed in OPTIMATE is considered intrinsically low risk, given that all of the advice points to be offered to patients' attending hospital medical staff and GPs are evidence-based and may be accepted or rejected by the patients' hospital doctors or GPs as they see fit.

Nevertheless, errors may possibly occur if primary researchers use patients' data incorrectly when applying STOPP/START criteria or Stockley's drug interaction software in the detection of drug-drug and drug-disease interactions.

Any actual or suspected significant adverse events experienced by patients arising out of application of the DI will be reported by the primary researcher to the following personnel within 24 hours of detection:

- (i) The trial PI.
- (ii) The local trial co-PI where the adverse event has been detected.
- (iii) The independent trial monitor.

The PI will co-ordinate an online discussion of the suspected adverse event within 48 hours of receiving notice of the event with the local trial PI, the primary researcher who has reported the adverse event and the independent trial monitor. If there is consensus that a clinically significant adverse clinical event arising out of applying the intervention has occurred, the adverse event will be reported to the TSC. The TSC chairperson will convene a meeting of the TSC within one week of notification to examine the details of reported potential adverse event and report back to the TMG within 24 hours of its deliberations.

Any adverse event deemed potentially attributable to incorrect/erroneous application of the DI, in the judgement of the local trial co-PI, will be investigated fully by the independent trial monitor within 2 weeks of the adverse event report.

An electronic record of all reported adverse events possibly relating to the application of the DI will be kept securely at the UCC Clinical Research Facility as part of the OPTIMATE trial record for further scrutiny/examination.

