A recent multi-centre randomized clinical trial (RCT) called SENATOR ([name] et al., 2020) examined the effect of a software intervention for applying STOPP/START PIM and PPO criteria (version 2; [name] et al., 2015) along with potentially adverse drug-drug and drug-disease interaction identification in hospitalized multi-morbid older patients on incident ADRs within 14 days of randomization. The trial which eventually randomized 1537 patients showed no difference in ADR incidence between intervention patients (24.5%) and control patients receiving standard pharmaceutical care (24.8%). Importantly, the overall implementation rate of software-generated medication recommendations by attending clinicians in their patients' medication lists was only 15% in the intervention arm. A previous single centre clinical trial had shown that delivery of STOPP/START recommendations in person by a trained physician resulted in 81.2% implementation of STOPP recommendations and 87.4% implementation of START recommendations (O'Connor et al.); the number needed to treat (NNT) to prevent one non-trivial incident ADR in that trial was eleven. A parallel study of STOPP/START recommendations (as part of a multi-faceted, software-supported medication optimizing intervention) being delivered in person by a clinical pharmacist resulted in STOPP recommendations being applied in 39.2% and START recommendations in 29.5% of cases

OPTIMATE Trial

Principal Investigator: [name] [name]

([name] et al.). This disparity has raised important questions about the impact of pharmacists in optimizing hospitalized older multi-morbid patients' medications (Dalton et al.).

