Within 72 hours of admission, patients who are potentially suitable for trial enrolment will be approached by the primary researchers (PRs) and informed about OPTIMATE in outline. If they meet inclusion criteria and do not have exclusion criteria, they will be asked to provide informed consent to trial enrolment. Recommended best practice for assessment of decision-making capacity of older patients who may be suitable for the OPTIMATE trial, involves formal assessment of capacity. Where necessary, the patient's mental capacity will be evaluated using the **OPTIMATE Decision-Making Capacity Functional Assessment** guidelines document in the OPTIMATE Manual of Operations. The patient will then be randomized to either the control arm (usual pharmaceutical care), pharmacist-delivered DI arm or physician-delivered DI arm of the trial. Randomization will proceed in a 1:1:1 ratio. The randomization process will be performed electronically using Castor EDC's block randomization algorithm. Patient enrolment will be sequential. With individual level randomization, there is the theoretical risk of control group contamination. This is where both control and intervention patients could be under the care of the same physician, thereby presenting a risk of medication advice learnings in intervention patients being applied unwittingly to control patients. However, in practice, as was seen in the pre-SENATOR observation study (Lavan et al.), variation in reported incidence of ADRs across various medical and surgical specialties in the 6 multi-national participating clinical sites was so large that meaningful cluster randomization was considered both impractical and unnecessary. Furthermore, in the SENATOR trial itself ([name] et al.), although uptake of medication optimization advice was generally poor, there was no evidence of contamination of the control population.

Randomization will be stratified by study site and by admitting service type (i.e. medical vs. surgical). The stratum-specific randomization lists will be generated electronically within Castor EDC, using a validated variable block randomization model. Once a patient has given consent and been enrolled onto the study, their data will be irreversibly added to the study database. From this point, the

primary researchers will receive randomization outcomes immediately upon activating the randomization request on the electronic Case Report Form (eCRF) within the Castor EDC.

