6.3 Safety outcomes (if relevant)

FORTA criteria (Kuhn-Thiel et al.) will be applied at baseline, at discharge, at day 30 and at day 180. FORTA criteria are validated explicit indicators of medication appropriateness. FORTA criteria category D in particular identify those medications that should be avoided in individual cases. Other FORTA labels range from A (indispensable) to B (beneficial), to C (questionable). FORTA criteria will provide an objective measure of medication safety in OPTIMATE. Patients in the 3 arms of the trial will be compared in terms of proportions with FORTA category A, B, C and D medications as indicators appropriateness/inappropriateness of medication.

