7.0 Data Management and Statistical Analysis

7.1. Data Management

The research team will engage closely with HRB data stewards based in the Statistics and Data Analysis Unit (SDAU) of the UCC HRB CRF-C. Before study initiation, study staff will be instructed by members of the SDAU on data collection, organization and eCRF entry techniques that adhere to the FAIR data principles and will guide development of the study data management plan.

The data obtained in OPTIMATE will include details of patients' age, sex, physical function, cognitive function, clinical diagnoses, medications, drug doses, laboratory test results indicating kidney and liver function, quality of life and survival at follow-up. Overall, the study will enroll approximately 1400 patients across three participating medical centres. The entire data collection is not expected to exceed 100 GB of digital storage.

Data collection will be performed using a third-party electronic data capture (EDC) system ensuring consistent data entry, documentation and security between research sites. Where applicable, variable data measurements will be recorded using international standardized units. All variables are to be recorded within Comma Separated Value (.csv) data tables. Data files will include metadata identifying title, creator, keywords etc. in line with the Dublin Core Metadata Initiative alongside accompanying data dictionaries which will be developed in parallel. Medical coding of adverse events (MedRA) and medications (WHODrug) will be enacted as part of the EDC platform. Throughout the OPTIMATE study, routine data visualization and exploration approaches using the R statistical computing and graphics language will be performed. This will allow for the development of standardized documentation of both data review and reporting processes, in collaboration with the SDAU, that is both reproducible and linked to version control strategies.

Data storage and back-up will be dictated by the EDC supplier allowing for two-factor authentication and establishment of defined user access permissions and audit trails. All OPTIMATE trial data will be collected electronically and entered on a bespoke trial proforma. Once verified as

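### Adverse events are reported and kept only when suspected of arising from the intervention, so control patients contribute none and adverse-event rates cannot be compared between arms

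*Combined protocol and SAP*

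**What the plan says.** Section 11.1 sets the only adverse-event rule in the document: "Any actual or suspected significant adverse events experienced by patients arising out of application of the DI will be reported by the primary researcher". The report goes to the trial PI, the local co-PI and the independent trial monitor within 24 hours. The Trial Steering Committee (TSC) is told afterwards, on a condition: "If there is consensus that a clinically significant adverse clinical event arising out of applying the intervention has occurred". The archive has the same scope as the report: "An electronic record of all reported adverse events possibly relating to the application of the DI will be kept securely".

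The same section describes the background: "Adverse clinical events are expected to occur with a substantially high frequency in the patient population participating in OPTIMATE".

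The person who reports is not blinded. Under 4.3, "primary researchers will receive randomization outcomes immediately upon activating the randomization request".

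Tables 1a and 1b contain no adverse-event row at any visit, and section 7.2 plans no adverse-event analysis. Section 7.1 nevertheless says: "Medical coding of adverse events (MedRA) and medications (WHODrug) will be enacted as part of the EDC platform". It does not say which events, in which arms or at which contacts.

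The section on safety outcomes relies on medication appropriateness: "FORTA criteria will provide an objective measure of medication safety in OPTIMATE". This is compared across the three arms.

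Sections 6.1, 6.2 and 7.2 do compare each active arm with control on unscheduled readmission, ED attendance, all-cause mortality, first long-term residential care and EQ-5D-5L.

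**The concern.** A report under 11.1 needs a suspected link to the definitive intervention (DI). A control patient has no DI, so no control event can qualify. What the trial collects under this rule is therefore a list from the two active arms, filtered first by a researcher who knows the allocation.

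In frail, multimorbid patients with many background events, looking at single cases is a poor way to tell an intervention-caused event from one that would have happened anyway. Comparison with a concurrent control group is the tool for that, and the rule removes it for adverse events.

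At stake is what the trial report can say about safety. A statement that the DI caused few adverse events would rest on a one-sided list. A modest excess of in-hospital or non-serious harm could pass as expected background.

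**Working it through.** **1. What the 11.1 rule can estimate.** Write the reported adverse-event risk difference as (DI reports / DI patients) − (control reports / control patients). The second numerator is zero by definition. The difference therefore equals the attributed rate in the DI arm and carries no information about background. Sample size does not change this.

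**2. Arm sizes (section 4.3).** Inputs: 20% versus 12%, two-sided 5%, 80% power.
- Unpooled normal formula: n = (1.96 + 0.8416)² × (0.20×0.80 + 0.12×0.88) / 0.08² = 325.7. The pooled version gives 329 and the arcsine version 324.9.
- The plan's 324 per arm is reproduced closely; its power by the pooled formula is 79.5%.
- 972 / (1 − 0.30) = 1388.6, so 1389 randomized, or 463 per arm. This matches the plan.

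**3. How large the background could be.** The documents give no adverse-event rate for this trial. Section 2.1 cites 24.8% of control patients with an adverse drug reaction within 14 days in the earlier software-based trial. Taking that as an illustrative assumption:
- per arm: 0.248 × 463 = 114.8, about 115 patients;
- both DI arms: 0.248 × 926 = 229.6, about 230 patients.

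These would occur with no DI effect, and any DI-caused events would have to be recognized among them one by one.

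**4. What recording in all arms would give.** The 95% half-width for one active arm against control is 1.96 × √(2 × 0.248 × 0.752 / n).
- n = 463: 5.6 percentage points.
- n = 324: 6.7 percentage points.

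These hold only if the recorded harms have a rate near 24.8%. The list proposed below may have a different one.

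**5. What the existing all-arm outcomes can show.** Smallest absolute increase detectable with 80% power, two-sided 5%, one active arm against control:

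| Control rate | 324 per arm | 463 per arm |
|---|---|---|
| 5% (assumed) | 6.0 points | 4.9 points |
| 10% (assumed) | 7.6 points | 6.3 points |
| 20% (the plan's 180-day readmission figure) | 9.5 points | 7.9 points |

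Sensitivity to serious harm is limited but present.

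**6. What these outcomes leave out.**
- They are defined from discharge, whereas baseline, when the DI starts, falls within 72 hours of admission.
- Readmission and ED attendance are all-cause. If the DI prevents a share *b* of patients' events and causes a share *h*, the trial estimates only *h* − *b*. No cause is recorded that would separate them.
- Laboratory results and the Barthel Index are scheduled at baseline and pre-discharge in both tables, but neither is named as an outcome or safety measure, and no comparison is planned.
- FORTA would show loss of category A drugs or addition of category D drugs. It does not show the clinical consequence of a drug change.

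**The case against.** The strongest reply is that the most serious harms are already compared. Death, readmission, ED attendance and residential care are collected in all three arms without attribution and are reported with odds ratios and 95% intervals. This stands. A reader might infer from 11.1 that the trial cannot show whether the DI causes harm at all; the documents do not support that.

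Nor do they support saying that the TSC has no comparator. Section 9.0 has it assess emerging data and the critical efficacy endpoints as well as safety data.

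The filter is also milder than it may look. Suspicion is enough for a first report, three parties see it, and every reported event possibly related to the DI is kept whether or not consensus follows. This too stands. It does not bring in control events, and it cannot recover an event that the researcher did not suspect.

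The coding sentence in 7.1 leaves room for wider capture, but no section provides for it.

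The plan calls the DI low risk because physicians may reject the advice. One might set against this that physician-delivered advice "resulted in 81.2% implementation of STOPP recommendations and 87.4% implementation of START recommendations". That figure is selective: section 2.1 also gives 39.2% and 29.5% for pharmacist delivery and 15% for the software trial, and the high-uptake trial reported one non-trivial reaction prevented per eleven patients treated. The present point does not depend on uptake.

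**Conclusion.** The concern holds in a limited form. As written, adverse-event rates cannot be compared between arms. Serious harm can be seen only through all-cause post-discharge outcomes, in which DI harm and benefit net out. In-hospital events and milder harms that do not reach those outcomes have no planned control comparison.

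The first part follows from the text alone and needs no assumed rate. The sizes (about 115 background events per arm; ±5.6 or ±6.7 points) rest on borrowing a 14-day rate from another trial, and the ±5.6 figure also assumes that all 463 per arm are assessed. The primary efficacy comparison is unaffected. This is an inexpensive improvement that should be made, because the plan's present adverse-event reports would not support a safety conclusion.

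**What to change.** Amend section 11.1 and Tables 1a and 1b as follows.

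- Record a short, prespecified list of harms, chosen and defined by the trial team, on identical terms in all three arms. Use the existing pre-discharge, 1-month and 6-month contacts. The pre-discharge entry should cover events since randomization, so that in-hospital harm is included. Record regardless of any suspected link to the DI.
- For each death, unscheduled readmission and ED attendance already ascertained, record the main cause.
- Have any judgement of drug-relatedness made by the outcome assessors whom section 4.3 says are blinded. If that is not feasible, leave it out of the between-arm comparison: DI patients can be expected to have more drug changes, so unblinded suspicion would differ by arm.
- Add to section 7.2 a by-arm table of these harms with risk differences and 95% confidence intervals, alongside FORTA. State in 7.1 which events are coded.
- Keep the 24-hour route for suspected DI-related events as an addition.

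The cost is a few eCRF fields, slightly longer contacts, some blinded assessor time if relatedness is judged, and one more table. No visit is added. Two limits remain: precision is modest, as shown above, and a main cause obtained by telephone will sometimes be uncertain.

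### The only event-level route that Section 11.1 defines to the committee acting as DMC depends on consensus about causation, so an event the independent monitor considers related can be held back from prompt review

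*Combined protocol and SAP*

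**What the plan says.** Section 11.1 (Adverse Event reporting) covers actual or suspected significant adverse events arising from the definitive intervention (DI). Such an event "will be reported by the primary researcher to the following personnel within 24 hours of detection": the trial PI, the local co-PI and the independent trial monitor. The TSC is not on that list. Within 48 hours of notice the PI co-ordinates an online discussion "with the local trial PI, the primary researcher who has reported the adverse event and the independent trial monitor". The next step is conditional: "If there is consensus that a clinically significant adverse clinical event arising out of applying the intervention has occurred", then "the adverse event will be reported to the TSC". The TSC chair convenes a meeting within one week of notification, and the TSC reports back to the Trial Management Group within 24 hours of its deliberations.

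The same section names a hazard of its own: "errors may possibly occur if primary researchers use patients' data incorrectly when applying STOPP/START criteria" or the interaction software. An event potentially attributable to erroneous application of the DI, in the local co-PI's judgement, "will be investigated fully by the independent trial monitor within 2 weeks of the adverse event report". An electronic record of all reported events possibly related to the DI is kept at the UCC Clinical Research Facility.

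Section 9.0 states that a separate DMC is not needed because the trial is low-risk. It continues: "It is proposed that the TSC will also undertake the core roles and responsibilities of a DMC". Those roles are "to regularly assess and advise on the data emerging from the trial, relevant safety data" and the critical efficacy endpoints, and to recommend whether the trial should continue, be modified or stop. TSC meetings are proposed every 3 months.

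**The concern.** A causation filter stands in front of the only body asked to recommend continuing, modifying or stopping the trial. Most of the people operating it belong to the trial team. One of them is a primary researcher, the role whose possible error Section 11.1 gives as the hazard. The one independent participant has a seat in the discussion but no stated way to act on a dissenting view.

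Section 11.1 expects adverse events to be frequent in this old, multimorbid population, whatever the arm. A single event will often be hard to attribute to a medication recommendation. A recurring problem may therefore show only when suspected events are read together, and suspected events without agreed causation are the ones this trigger can withhold. What is at stake is timely safety oversight. The endpoints and their analysis are untouched.

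**Working it through.** The plan gives no figure on this point, so the check is a reading of the text, with two small counts.

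**1. Who decides.** Section 11.1 lists four roles in the discussion: PI, local PI, reporting primary researcher and independent monitor. Trial team: 3. Independent: 1. This takes the PI, who co-ordinates the discussion, as a party to the consensus. If the PI is also the local PI for a site, the count becomes 2 to 1 and the argument is the same.

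**2. What must be agreed.** The trigger has two parts: that the event is clinically significant, and that it arose from applying the intervention. Suspicion is enough for the 24-hour report but not for the TSC.

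**3. What consensus could mean.** The term is undefined, so both ordinary readings were tried.
- Unanimity: any one of the 3 trial-team members can stop a report that the monitor supports.
- General agreement: the 3 can outweigh the 1.

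On either reading an event that the monitor considers related can fail the trigger. No rule covers that case.

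**4. Other ways to the TSC.**
- *Error investigation (11.1).* It starts on the local co-PI's judgement and covers only incorrect application of the DI. Harm from correctly applied advice falls outside it. No report to the TSC is stated.
- *Electronic record (11.1).* It holds all reported events possibly related to the DI, with or without consensus. No transmission to the TSC is stated.
- *Deviation reporting (11.2).* Deviations that could affect participant safety go to the sponsor. The TSC is not named.
- *General remit (9.0).* The TSC is to assess relevant safety data regularly. The plan does not say which listings it receives or from whom.

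Count of defined event-level routes to the TSC: 1, and it is conditional on consensus.

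**5. What the condition costs in time.** With consensus, a TSC meeting follows within 7 days of notification. Without consensus, the next scheduled occasion is the quarterly meeting, up to about 3 months away, and the plan does not say that the event would be tabled there.

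**The case against.** The case for leaving Section 11.1 alone has substance. The DI is advice that hospital doctors and GPs may reject, so a light safety structure is reasonable. The monitor receives every report within 24 hours and sits in the discussion. The reporting researcher has already flagged the event, so is the participant least likely to block it, and the plan does not say that this person delivered the DI to that patient. Possible error has its own, lower threshold and is investigated by the monitor. Nothing forbids the monitor from approaching the TSC. All of this stands, and it limits the point to a safety-governance improvement. It does not explain why causation must be agreed before the TSC sees an event promptly, or what happens when the monitor disagrees.

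A reader might infer more than the documents support:
- *That the TSC sees only events with consensus.* Its general remit and the stored record leave room for other events to surface at a periodic review. The plan does not say that they will, but it does not exclude it.
- *That a single dissent is a veto.* This holds only if consensus means unanimity.
- *That escalation requires the investigators to accept blame.* The criterion is significance and causation; fault is handled separately.
- *That the decision to have no DMC relies on this route.* The stated reason is low risk: evidence-based advice left to the attending physician.
- *That the deadlines conflict.* Counted from the report, and assuming immediate TSC notification, the consensus route ends by day 2 + 7 + 1 = 10, against 14 days for the error investigation. Both are upper limits on parallel processes with different purposes, and neither is required to precede the other.
- *That a blocking rate can be calculated.* The documents give no probabilities of attribution, and opinions formed in a joint discussion are not independent.

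**Conclusion.** The point holds in a limited form. Section 11.1 defines one event-level route to the committee acting as DMC. It is conditional on consensus in a group of three trial-team roles and one independent monitor, and an event that the monitor considers related can be held back from prompt review. The size is structural: one conditional route, no rule for disagreement, and a possible change from review within a week to a quarterly meeting at which tabling is not guaranteed.

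This rests on two assumptions: that all four roles are party to the consensus, and that the absence of a stated route means the plan does not provide one. It describes what the text permits; nothing in the documents shows that events would be suppressed. The plan should be changed because the safeguard is cheap and the TSC is the only body with this remit, but the point does not threaten the trial's results.

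**What to change.** Amend Section 11.1 in three places, with a cross-reference in Section 9.0.
1. Replace the consensus trigger. An event goes to the TSC if the independent monitor alone, or any one participant in the discussion, considers it possibly related to the DI. The discussion still takes place, and any differing views go to the TSC with the report.
2. Allow the monitor, as well as the local co-PI, to open the investigation of erroneous application, and send its result to the TSC.
3. Table the existing electronic log of all reported events at each 3-monthly TSC meeting, and name it in Section 9.0 as part of the safety data that the TSC reviews.

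The cost is a short protocol amendment and some additional TSC notifications, each of which calls for a meeting within a week under the present rule. The discussion group, the log and the quarterly meetings are already in the plan, and no new data are collected.
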